#### **6.2.7.2. ADA titer**

For patients who are ADA ever positive, the maximum observed ADA titer for a patient will be summarized, overall and by ADA subcategories (baseline ADA positive, treatment-boosted ADA, treatment-induced ADA, transient ADA response, persistent ADA response) of patients having each discrete maximum titer value will be tabulated. The denominator to calculate the percentages will be the total number of patients in the associated ADA subcategory.

For patients with treatment-induced ADA, a cross tabulation of duration of ADA response and maximum ADA titer will be provided. The following categories for duration of ADA response will be used:  $\leq 1$ ,  $>1$  to  $\leq 3$ ,  $>3$  to  $\leq 5$ ,  $>5$  to  $\leq 7$ ,  $>7$  to  $\leq 13$ ,  $>13$  to  $\leq 16$ ,  $>16$  to  $\leq 25$ ,  $>25$  weeks. In this categorization, the censoring in duration of ADA response is ignored.

#### **6.2.7.3. Analysis of PK and safety by immunogenicity status**

The following ADA and nAb status will be used for the analyses described below.

ADA

- ADA ever-positive versus ADA never-positive;
- ADA: treatment-induced ADA versus ADA never-positive or baseline ADA positive.

## nAb

- nAb ever-positive versus nAb never-positive;
- nAb: treatment-induced nAb versus nAb never-positive or baseline nAb positive.

Data listings will include immunogenicity data together with relevant PK, safety and efficacy data.

## PK parameters and immunogenicity status

The following analyses will include patients in both the immunogenicity analysis set and in the PK parameter analysis set. The PK endpoints pertinent to the immunogenicity analyses are  $C_{\text{trough}}$  and  $C_{\text{max}}$ .

Blood samples for avelumab PK will be collected pre-dose (within 2 hours before the start of avelumab/placebo infusion) and at the end of infusion (immediately before until 10 minutes after the end of avelumab/placebo infusion) on Days 1 of the Lead-in Phase and Days 8, and 25 of the CRT Phase.

$C_{\text{trough}}$  and  $C_{\text{max}}$  will be summarized descriptively (n, mean, SD, CV, median, minimum, maximum, geometric mean, its associated CV, and 95% CI) by nominal time and ADA status. Linear-linear and log-linear plots of mean and median for  $C_{\text{trough}}$  and  $C_{\text{max}}$  over nominal time and by ADA status will be presented.

Among patients with treatment-induced ADA, analyses will be conducted to assess whether  $C_{\text{trough}}$  and  $C_{\text{max}}$  have any changes before and after the first positive ADA assessment. To be included in this analysis, patients must have the same PK parameter available both before and after the first positive ADA assessment. Relative PK day will be calculated as:

$$(\text{PK assessment nominal day}) - (\text{first positive ADA assessment nominal day}).$$

Nominal day is the protocol scheduled timing for an assessment. For example, if  $C_{\text{trough}}$  is collected on Day 8 of CRT Phase and the first positive ADA result is observed on Day 25 of CRT Phase, then the relative PK day for this  $C_{\text{trough}}$  is -17. Linear-linear and log-linear plots of mean and median for  $C_{\text{trough}}$  and  $C_{\text{max}}$  over relative PK day will be presented.

As data permit, the analyses described above will be repeated for nAb.

## Safety and immunogenicity status

The following analyses will include patients in the immunogenicity analysis set.

The frequency (number and percentage) of patients with each of the following will be presented by ADA status.

- TEAEs, by SOC and PT;
- TEAEs leading to dose reduction of avelumab, by SOC and PT;

- TEAEs leading to discontinuation of avelumab, by SOC and PT;
- TEAEs leading to discontinuation of study treatment by SOC and PT;
- Grade  $\geq 3$  TEAEs, by SOC and PT;
- SAEs, by SOC and PT;
- IRRs associated with avelumab, by PT.

For patients who had at least one IRR and have treatment-induced ADA, time related to first onset of an IRR (infusion 1, infusion 2, infusion 3, infusion 4 or later) will be summarized taking into account whether the IRR occurred on or after the first ADA positive assessment or whether the IRR occurred before the first ADA positive assessment.

As data permit, the analyses described above will be repeated for nAb.

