**Table 6. Treatment Modification for Symptoms of Avelumab/Placebo Infusion-Related Reactions**

NCI CTCAE Grade	Treatment Modifications
Grade 1 – mild Mild transient reaction; infusion interruption not indicated; intervention not indicated.	
 
Decrease the investigational product infusion rate by 50% and monitor closely for any worsening.
 

Grade 2 – moderate Therapy or infusion interruption indicated but responds promptly to symptomatic treatment (eg, antihistamines, NSAIDs, narcotics, IV fluids); prophylactic medications indicated for ≤24 hours.	
 
Stop investigational product infusion.
 
Resume infusion at 50% of previous rate* as soon as infusion-related reaction has resolved or decreased to at least Grade 1 in severity, and monitor closely for any recurrence or worsening.
 

Grade 3 or Grade 4 – severe or life-threatening Grade 3: Prolonged (eg, not rapidly responsive to symptomatic medication and/or brief interruption of infusion); recurrence of symptoms following initial improvement; hospitalization indicated for clinical sequelae. Grade 4: Life-threatening consequences; urgent intervention indicated.	
 
Stop the investigational product infusion immediately and disconnect bag infusion tubing from the patient.
 
Investigational product treatment must be permanently discontinued.
 

IV=intravenous, NCI-CTCAE=National Cancer Institute Common Terminology Criteria for Adverse Event, NSAIDs=nonsteroidal anti-inflammatory drugs.

\*If avelumab/placebo infusion rate has been decreased by 50% due to an infusion reaction, it must remain decreased for the next scheduled infusion. If no infusion reaction is observed at the next scheduled infusion, the infusion rate may be returned to baseline at subsequent infusions.

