### 5.2.7. Definition of on-treatment period

Safety endpoints will be summarized based on the on-treatment period unless otherwise specified.

On-treatment period is defined as the time from the first dose of study treatment through minimum (30 days + last dose of study treatment, start day of new anti-cancer drug therapy – 1 day).

Safety data collected outside the on-treatment period as described above will be listed and flagged in listings but will not be summarized.

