**Table 22. Patients Characterized Based on Anti-Drug Antibody Results (ADA Status)**

Category	Definition	Patients at Risk (Denominator for Incidence)
ADA never-positive	No positive ADA results at any time point; ADA-negative patients (titer < cutpoint)	Number of patients with at least one valid ADA result at any time point
ADA ever-positive	At least one positive ADA result at any time point; ADA-positive patients (titer ≥ cutpoint)	Number of patients with at least one valid ADA result at any time point
Baseline ADA positive	A positive ADA result at baseline	Number of patients with valid baseline ADA result
Treatment-boosted ADA	A positive ADA result at baseline and the titer ≥ 8×baseline titer at least once after treatment with avelumab	Number of patients with valid baseline ADA results and at least one valid post-baseline ADA result
Treatment-induced ADA	Patient is ADA-negative at baseline and has at least one positive post-baseline ADA result; or if patient does not have a baseline sample, the patient has at least one positive post-baseline ADA result	Number of patients with at least one valid post-baseline ADA result and without positive baseline ADA result (including missing, NR)
Transient ADA response	If patients with treatment-induced ADA have (a single positive ADA result or duration between first and last positive result <16 weeks) and ADA result at the last assessment is not positive.	Number of patients with at least one valid post-baseline ADA result and without positive baseline ADA result (including missing, NR)
Persistent ADA response	If patients with treatment-induced ADA have duration between first and last positive ADA result ≥16 weeks or a positive ADA result at the last assessment	Number of patients with at least one valid post-baseline ADA result and without positive baseline ADA result (including missing, NR)

ADA: anti-drug antibody, NR = not reportable.

Patients will be characterized into different nAb categories based on the criteria in Table 23. For nAb, treatment-boosted is not applicable since no titer result is available.

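### AE tables by ADA status fix the status from the whole study but count AEs from first dose, so time on treatment biases them: low for discontinuation, mildly high for cumulative rows

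*SAP*

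**What the plan says.** SAP 6.2.7.3 sets two contrasts for the safety tables: "ADA ever-positive versus ADA never-positive", and treatment-induced ADA against patients who were never positive or were positive at baseline. Under Table 22, ever-positive means "At least one positive ADA result at any time point". Never-positive means no positive result, and its denominator needs only one valid ADA result at any time. The immunogenicity analysis set (SAP 4.3.4) likewise needs only one sample.

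The statistic is plain: "The frequency (number and percentage) of patients with each of the following will be presented by ADA status". Seven rows follow: all TEAEs, dose reduction, "TEAEs leading to discontinuation of avelumab, by SOC and PT", discontinuation of study treatment, Grade ≥3 TEAEs, SAEs, and avelumab IRRs. The tables are repeated for neutralizing antibodies as data permit. The AE window (SAP 5.2.7) is not tied to antibody status: "On-treatment period is defined as the time from the first dose of study treatment through minimum (30 days + last dose of study treatment", or the day before new anti-cancer drug therapy if that comes first.

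Order in time is used in two other places of the same section. The PK analysis compares values before and after the first positive ADA result. The summary of first IRR onset is split the same way, for treatment-induced patients only.

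The sampling schedules differ. Protocol Table 3, footnote 20, draws ADA on Day 1 of Maintenance Cycles 1 and 2, then every 3 cycles on treatment, at EOT and 30 days after EOT. SAP 6.2.7 lists only Lead-in Day 1 and CRT Days 8 and 25, and SAP 6.2.7.1 calls CRT Day 25 the last planned assessment.

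**The concern.** The column a patient falls in is decided by events after the AEs being counted. Someone who stops at week 6 has little time to turn positive and few samples to show it, and tends to be filed as never-positive. Someone who completes a year of Maintenance has the full chance to convert and also a much longer window in which to collect AEs. Two consequences follow when ADA does nothing. Discontinuation looks rarer in ADA-positive patients, because stopping early prevents conversion from being seen. Any AE that accumulates with exposure looks commoner in them. AEs that began before the first positive result are also filed under ADA-positive.

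Assessing ADA is a secondary objective, and these rows are the SAP's planned look at whether ADA matters for safety. A table meant to raise hypotheses can then raise false ones, in opposite directions on the same page.

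**Working it through.** The documents give no rate, power or effect for this table, so there is no planned figure to reproduce. The check asks what the table would show if ADA had no effect on any AE.

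**Inputs from the documents.** With Lead-in Day 1 as day 1, CRT Day 8 is day 15 and CRT Day 25 is day 32. Maintenance starts about day 71 (8 + 63), and the last dose is about day 435 (71 + 364). Stopping avelumab for a TEAE: 14.0% (244/1738, Protocol 1.2.2, monotherapy). IRR: 25.3% (439/1738).

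**Assumptions, not in the documents.** Eventual ADA 5%, 15% or 30%; onset early (mean 45 days) or uniform over treatment; other stopping 30%; Grade ≥3 AE 60%; AE hazard constant or falling with time. Three sampling plans were used: the protocol's with the EOT and 30-day samples, the protocol's without them, and the SAP's.

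**One case by hand** (15% ADA, uniform onset, constant hazard, EOT and 30-day samples included):
- Hazards over 435 days: −ln 0.86 = 0.151 for AE stopping and −ln 0.70 = 0.357 for other stopping, sum 0.5075.
- Completers: 0.86 × 0.70 = 0.602. AE stoppers: (0.151/0.5075) × 0.398 = 0.118.
- Mean stopping time among stoppers, as a fraction of 435 days: 1/0.5075 − 0.602/0.398 = 0.458. Adding 30/435 for post-treatment sampling gives 0.527.
- Chance of being seen positive: 0.15 for completers; 0.15 × 0.527 = 0.079 for stoppers.
- Ever-positive overall: 0.602 × 0.15 + 0.398 × 0.079 = 0.122.
- AE discontinuation among ever-positive: 0.118 × 0.079 / 0.122 = 7.7%. Among never-positive: 0.118 × 0.921 / 0.878 = 12.4%. **Risk ratio 0.62 with no ADA effect.** A simulation of one million patients gave the same figures.

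**Cumulative row, same case.** Completers are 0.0903/0.122 = 74% of ever-positive patients but 0.512/0.878 = 58% of never-positive patients. A completer's Grade ≥3 risk is 1 − 0.40^(465/435) = 62%; a stopper's is lower because the window is shorter. The simulation gave 58.1% against 51.2%, risk ratio 1.13.

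**Range over the scenarios.**

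| Row | Risk ratio, ever- vs never-positive, no ADA effect |
|---|---|
| Discontinuation of avelumab | 0.36–0.97 (one exception, 1.03, with 0.4% positive) |
| Grade ≥3 TEAE | 1.02–1.18 |
| IRR, modelled as unrelated to time on treatment | 0.99–1.02 |

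With early onset and EOT and 30-day samples, the discontinuation ratio is 0.86–0.97. Between 9% and 78% of Grade ≥3 AEs in the ever-positive column began before the first positive result. A second set of no-effect runs, which included AEs clustered in the CRT Phase, gave 0.23–0.95 for discontinuation and 1.02–1.15 for Grade ≥3.

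**Does a remedy work?**
- An unstratified split of patient-time still gave 0.51–0.82 when the AE hazard fell with time, and 0.32–0.71 when AEs clustered in the CRT Phase.
- Time-updated status compared within treatment phase gave 0.97–1.01 when hazard was steady within phase and 0.86–0.96 when it fell continuously.
- Within 5-day intervals since first dose (15% ADA) it gave 0.97–1.01 for discontinuation, apart from 1.09 in one run with 1% positive (simulation noise), and 0.99–1.00 for Grade ≥3.

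**Schedule conflict.** CRT Day 8 to Day 25 is 17 days. On the SAP's draws, a patient negative at baseline could never reach the 16 weeks used for persistent ADA in Table 22, nor the category above 25 weeks in SAP 6.2.7.2.

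**The case against.** The case for leaving the tables alone has real content.

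- **They are exploratory.** SAP 3.5.1 describes safety analyses as generally hypothesis-generating. These tables are Arm A only and do not touch PFS or OS. This stands and limits the weight of the point.
- **Early stoppers are still sampled.** Under the protocol, EOT and 30-day samples are drawn. This shrinks the bias but does not remove it: the worked case includes those samples.
- **The size is unknown.** ADA incidence and onset are not in the documents, and with early onset the discontinuation bias is small. The 14.0% is a monotherapy figure; the head and neck cohort had 5.4% (Protocol 1.2.2.1).
- **IRR order is partly handled.** First IRR onset is split at the first positive result, and listings combine immunogenicity with safety data. But the IRR frequency row and every other row lack that split.
- **Baseline-positive patients** have no time before the antibody, so they dilute the problem in the ever-positive contrast.

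A reader might go further and infer three things that the documents do not support:

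- *That ADA will look protective throughout.* Only the two discontinuation rows lean that way. The cumulative rows lean the other way, and all-grade IRRs hardly move.
- *That a planned conclusion is wrong in sign, or a test has an inflated error rate.* The SAP plans counts and percentages here, with no test, interval or decision.
- *That severe IRRs drive the distortion.* After a Grade 3 or 4 reaction, "Investigational product treatment must be permanently discontinued", so the mechanism exists. But Protocol 1.2.2 reports Grade ≥3 IRRs in 12 of 1738 patients (0.7%), about 2 in 320, and the ADA tables have no separate Grade ≥3 IRR row.

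**Conclusion.** The point holds as a bias from time on treatment with row-specific direction. With no ADA effect, the planned tables tend to show ADA as protective for discontinuation (risk ratio about 0.2 to 0.97) and mildly harmful for cumulative AEs (1.02 to 1.18 for Grade ≥3 TEAEs, used as the model for all TEAEs and SAEs). The direction follows from the SAP's definitions. The size rests on assumed ADA incidence, onset, other stopping and AE hazard shape, and may be small if antibodies appear early. Primary and secondary efficacy inference is not affected. The change is worth making because the SAP already uses the first-positive date for PK and for first IRR onset, and a descriptive table that produces a signal under no effect does not serve its purpose. The mismatch between SAP and protocol ADA schedules is a separate, firmer defect.

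**What to change.** In SAP 6.2.7.3, for treatment-induced ADA (and nAb where repeated):

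1. Add a version of the AE rows with time-updated status. An AE counts as ADA-positive only if its onset is on or after the first positive sample; earlier time and events count as ADA-negative.
2. Report events per patient-time within treatment phase, using the phase windows already defined in SAP 6.6.1.1, or within finer intervals since first dose. Phase strata leave some bias if the hazard falls within a phase. A landmark is an alternative: classify by status at CRT Day 25 and count later AEs in patients still on treatment. Do not use an unstratified patient-time split.
3. Show baseline-positive patients as a separate group.
4. Show IRRs by infusion number from infusion 2 on, by ADA status at that infusion.
5. Reconcile the ADA sampling schedule in SAP 6.2.7 and 6.2.7.1 with Protocol Table 3, footnote 20.

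The existing crude table can stay, with a footnote that it is affected by time on treatment. The cost is SAP wording and modest extra programming. No new data are needed. With few ADA-positive patients the stratified rates will be imprecise.

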### 6.3. Other Endpoints

CCI [REDACTED]

[REDACTED]

[REDACTED]

CCI [REDACTED]

[REDACTED]

### 6.4. Subset Analyses

Subset analyses will be performed for PFS, OS, uOR and DR based on the FAS for the subgroups defined below.

The following subgroups will be defined and used for analyses:

- Randomization stratification factors
  - Tumor (T) stage (<T4 vs T4; T4=Reference);
  - Nodal (N) stage (N0/N1/N2a/N2b vs N2c/N3; N2c/N3=Reference);
  - HPV status (positive vs negative; negative=Reference) as measured by p16 expression by IHC.

- Age
  - Age < 65 years (Reference);
  - Age ≥ 65 years.
- Gender
  - Male (Reference);
  - Female.
- Race
  - White (Reference);
  - Asian;
  - Black or African American;
  - Other.
- Ethnicity
  - Hispanic or Latino;
  - Not Hispanic or Latino (Reference).
- Pooled Geographical Region
  - North America;
  - Western Europe (Reference);
  - Eastern Europe;
  - Asia;
  - Rest of the World (Australasia, Latin America, Africa and/or Middle East will be included as additional subgroups if including > 10% of the overall randomized population).
- ECOG Performance Status at Baseline
  - 0 (Reference);
  - 1.
- Subsite of Primary Diagnosis
  - Oral cavity (Reference);
  - Oropharynx;
  - Larynx;
  - Hypopharynx;
  - Other.

Subset analyses for PFS, OS and DR will use the primary censoring rules described in Sections 6.1.1.1 and 6.2.2.1. All the subgroup analyses are exploratory. Treatment arms will be compared for PFS and OS using a 2-sided unstratified log-rank test for each subgroup

level and the unstratified HR and its corresponding 95% CI will be computed per subgroup level.

All the subgroup analyses will be exploratory; no adjustment for multiplicity will be performed. In the case of a low number of patients within a category (<5% of the randomized population), the categories will be pooled.

To assess the heterogeneity of treatment effects for PFS and OS across the subgroup levels, two Cox regression model will be fitted with PFS or OS, respectively, as the dependent variable and subgroup, treatment, and with and without the treatment-by-subgroup interaction as explanatory variables.

- Model 1: factors + treatment + subgroup
- Model 2: factors + treatment + subgroup + treatment×subgroup-variable

A p-value for the interaction test (Wald's test) will be provided together with the HR and corresponding 95% CI for the interaction model parameter.

The HR for PFS and OS and corresponding 95% CIs for all subgroups will also be presented in a forest plot.

The ORR odds ratio for each subgroup and corresponding 95% CIs will also be presented in a forest plot for each treatment arm.

## **6.5. Baseline and Other Summaries and Analyses**

### **6.5.1. Baseline summaries**

The following analyses will be based on the FAS overall and separately by treatment arm.

#### **6.5.1.1. Demographic characteristics**

Demographic characteristics and physical measurements will be summarized by treatment arm using the following information from the 'Screening/Baseline Visit' eCRF pages.

- Demographic characteristics
  - Gender: Male, Female
  - Race: White, Black or African American, Asian, American Indian or Alaska Native, Native Hawaiian or other Pacific Islander, Other, Unknown
  - Ethnic origin:
    - Hispanic or Latino
    - Not Hispanic or Latino
  - Age (years): summary statistics

- Age categories:
  - < 65 years, ≥ 65 years;
  - < 65, 65-<75, 75-<85, ≥ 85 years.
- Pooled Geographical Region (as applicable):
  - North America;
  - Western Europe;
  - Eastern Europe;
  - Asia;
  - Rest of the World (Australasia, Latin America, Africa and/or Middle East will be included as additional pooled geographical regions if including > 10% of the overall randomized population).
- Geographic Region (as applicable):
  - North America;
  - Latin America;
  - Western Europe;
  - Eastern Europe;
  - Middle East;
  - Australasia;
  - Asia;
  - Africa.
- Eastern Cooperative Oncology Group (ECOG) Performance Status: 0, 1, 2, 3, and 4
- Physical measurements
  - Height (cm);
  - Weight (kg);
  - Body Mass Index (BMI) (kg/m^2);
  - Body Surface Area (BSA) (m^2).

Center codes will be used for the determination of the patient's geographic region.

The listing of demographics and baseline characteristics will include the following information: patient identifier, treatment arm, age, sex, race, ethnicity, height (cm), weight (kg), BMI (kg/m^2), BSA (m^2) and ECOG performance status.

#### **6.5.1.2. Medical history**

Medical history will be coded using the most current available version of Medical Dictionary for Regulatory Activities (MedDRA) and will be summarized from the 'Medical History' eCRF page. Medical history will be summarized as the numbers and percentages of patients

by MedDRA preferred term (PT) as event category and MedDRA primary system organ class (SOC) as summary category. Each patient will be counted only once within each PT or SOC.

Medical history will be displayed in terms of frequency tables: ordered by primary SOC and PT in alphabetical order.

### **6.5.1.3. Disease characteristics**

Information on disease characteristics collected on 'Primary Diagnosis', 'Substance Use' and modified RECIST eCRF pages will be summarized overall and by treatment arm. Summary statistics will be presented for the following.

From the 'Primary Diagnosis' eCRF page:

- Site of primary tumor
- Primary diagnosis (summarize all categories collected in the 'Primary Diagnosis' eCRF page)
- Time since initial diagnosis to date of randomization (months), defined as (date of randomization – date of initial diagnosis)/30.4375

From the modified RECIST eCRF page:

- Measurable disease (lesions) at baseline (Yes, No)
- Involved tumor sites at baseline

From the 'Substance Use' eCRF page:

- Smoking history (never smoker, former smoker, current smoker)

Listing of disease history will be provided with all relevant data (as collected on the 'Primary Diagnosis' and 'Substance Use' eCRF pages) and derived variables as above.

